## PROMIS Parent Proxy Profile v2.0 – Profile-25

Fatigue In the past 7 days...		Never	Almost Never	Sometimes	Often	Almost Always
PR3fatigue8r	My child was too tired to do sports or exercise.....	 1	 2	 3	 4	 5
PR4fatigue4r	My child was too tired to enjoy the things he/she likes to do.....	 1	 2	 3	 4	 5
Peer Relationships In the past 7 days...		Never	Almost Never	Sometimes	Often	Almost Always
PR3socabil9r	My child felt accepted by other kids his/her age .....	 1	 2	 3	 4	 5
PR4socabil12r	My child was able to count on his/her friends.....	 1	 2	 3	 4	 5
PR2socrole4r	My child and his/her friends helped each other out .....	 1	 2	 3	 4	 5
PR1socabil2r	Other kids wanted to be my child's friend..	 1	 2	 3	 4	 5
Pain Interference In the past 7 days...		Never	Almost Never	Sometimes	Often	Almost Always
PR2pain5r	My child had trouble sleeping when he/she had pain.....	 1	 2	 3	 4	 5
PR3pain2r	It was hard for my child to pay attention when he/she had pain .....	 1	 2	 3	 4	 5
PR2pain4r	It was hard for my child to run when he/she had pain.....	 1	 2	 3	 4	 5
PR1pain4r	It was hard for my child to walk one block when he/she had pain .....	 1	 2	 3	 4	 5

Pain Intensity In the past 7 days...	
px9033R1	How bad was your child's pain on average? .....
	 0  1  2  3  4  5  6  7  8  9  10 No pain Worst pain you can think of

Last Update: 26 July 2016

© 2010-2016 PROMIS Health Organization and PROMIS Cooperative Group

Page 2 of 2

**Profile 29+2: Adult Patient and Caregiver will complete**

PROMIS® 29+2 Profile v2.1 (PROPr)

Please respond to each question or statement by marking one box per row.

	Physical Function	Without any difficulty	With a little difficulty	With some difficulty	With much difficulty	Unable to do
PFA11	Are you able to do chores such as vacuuming or yard work? .....	 5	 4	 3	 2	 1
PFA21	Are you able to go up and down stairs at a normal pace? .....	 5	 4	 3	 2	 1
PFA23	Are you able to go for a walk of at least 15 minutes? .....	 5	 4	 3	 2	 1
PFA53	Are you able to run errands and shop? .....	 5	 4	 3	 2	 1
	Anxiety In the past 7 days...	Never	Rarely	Sometimes	Often	Always
EDANX01	I felt fearful .....	 1	 2	 3	 4	 5
EDANX40	I found it hard to focus on anything other than my anxiety .....	 1	 2	 3	 4	 5
EDANX41	My worries overwhelmed me .....	 1	 2	 3	 4	 5
EDANX53	I felt uneasy .....	 1	 2	 3	 4	 5
	Depression In the past 7 days...	Never	Rarely	Sometimes	Often	Always
EDDEP04	I felt worthless .....	 1	 2	 3	 4	 5
EDDEP06	I felt helpless .....	 1	 2	 3	 4	 5
EDDEP29	I felt depressed .....	 1	 2	 3	 4	 5
EDDEP41	I felt hopeless .....	 1	 2	 3	 4	 5
	Fatigue During the past 7 days...	Not at all	A little bit	Somewhat	Quite a bit	Very much
HI7	I feel fatigued .....	 1	 2	 3	 4	 5
AN3	I have trouble starting things because I am tired .....	 1	 2	 3	 4	 5

Fatigue						
In the past 7 days...		Not at all	A little bit	Somewhat	Quite a bit	Very much
FATEXP41	How run-down did you feel on average? .....	 1	 2	 3	 4	 5
FATEXP40	How fatigued were you on average? .....	 1	 2	 3	 4	 5
Sleep Disturbance						
In the past 7 days...		Very poor	Poor	Fair	Good	Very good
Sleep109	My sleep quality was .....	 5	 4	 3	 2	 1
In the past 7 days...		Not at all	A little bit	Somewhat	Quite a bit	Very much
Sleep116	My sleep was refreshing .....	 5	 4	 3	 2	 1
Sleep20	I had a problem with my sleep .....	 1	 2	 3	 4	 5
Sleep44	I had difficulty falling asleep .....	 1	 2	 3	 4	 5
Ability to Participate in Social Roles and Activities						
		Never	Rarely	Sometimes	Usually	Always
SRPPER11 CaPS	I have trouble doing all of my regular leisure activities with others.....	 5	 4	 3	 2	 1
SRPPER18 CaPS	I have trouble doing all of the family activities that I want to do.....	 5	 4	 3	 2	 1
SRPPER23 CaPS	I have trouble doing all of my usual work (include work at home).....	 5	 4	 3	 2	 1
SRPPER46 CaPS	I have trouble doing all of the activities with friends that I want to do.....	 5	 4	 3	 2	 1
Pain Interference						
In the past 7 days...		Not at all	A little bit	Somewhat	Quite a bit	Very much
PAININ9	How much did pain interfere with your day to day activities? .....	 1	 2	 3	 4	 5
PAININ22	How much did pain interfere with work around the home? .....	 1	 2	 3	 4	 5
PAININ31	How much did pain interfere with your ability to participate in social activities? .....	 1	 2	 3	 4	 5

**Pain Interference****In the past 7 days...**

		Not at all	A little bit	Somewhat	Quite a bit	Very much
PAININ34	How much did pain interfere with your household chores? .....	 1	 2	 3	 4	 5

**Cognitive Function - Abilities****In the past 7 days...**

		Not at all	A little bit	Somewhat	Quite a bit	Very much
PC6r	I have been able to concentrate .....	 1	 2	 3	 4	 5

PC27r	I have been able to remember to do things, like take medicine or buy something I needed.....	 1	 2	 3	 4	 5
-------	--	-------------------------------	-------------------------------	-------------------------------	-------------------------------	-------------------------------

**Pain Intensity****In the past 7 days...**

Global07	How would you rate your pain on average? .....	 0 No pain	 1	 2	 3	 4	 5	 6	 7	 8	 9	 10 Worst pain imaginable
----------	--	--	-------------------------------	-------------------------------	-------------------------------	-------------------------------	-------------------------------	-------------------------------	-------------------------------	-------------------------------	-------------------------------	---

# Mobile Application Rating Scale (MARS)- Caregiver/Patients Day 120 (Ages 10 or older)

## App Quality Ratings

The Rating scale assesses app quality on four dimensions. All items are rated on a 5-point scale from “1.Inadequate” to “5.Excellent”. Circle the number that most accurately represents the quality of the app component you are rating. Please use the descriptors provided for each response category.

### SECTION A

**Engagement – fun, interesting, customisable, interactive (e.g. sends alerts, messages, reminders, feedback, enables sharing), well-targeted to audience**

**1. Entertainment: Is the app fun/entertaining to use? Does it use any strategies to increase engagement through entertainment (e.g. through gamification)?**

- 1 Dull, not fun or entertaining at all
- 2 Mostly boring
- 3 OK, fun enough to entertain user for a brief time (< 5 minutes)
- 4 Moderately fun and entertaining, would entertain user for some time (5-10 minutes total)
- 5 Highly entertaining and fun, would stimulate repeat use

**2. Interest: Is the app interesting to use? Does it use any strategies to increase engagement by presenting its content in an interesting way?**

- 1 Not interesting at all
- 2 Mostly uninteresting
- 3 OK, neither interesting nor uninteresting; would engage user for a brief time (< 5 minutes)
- 4 Moderately interesting; would engage user for some time (5-10 minutes total)
- 5 Very interesting, would engage user in repeat use

**3. Customisation: Does it provide/retain all necessary settings/preferences for apps features (e.g. sound, content, notifications, etc.)?**

- 1 Does not allow any customisation or requires setting to be input every time
- 2 Allows insufficient customisation limiting functions
- 3 Allows basic customisation to function adequately
- 4 Allows numerous options for customisation
- 5 Allows complete tailoring to the individual's characteristics/preferences, retains all settings

**4. Interactivity: Does it allow user input, provide feedback, contain prompts (reminders, sharing options, notifications, etc.)? Note: these functions need to be customisable and not overwhelming in order to be perfect.**

- 1 No interactive features and/or no response to user interaction
- 2 Insufficient interactivity, or feedback, or user input options, limiting functions
- 3 Basic interactive features to function adequately
- 4 Offers a variety of interactive features/feedback/user input options
- 5 Very high level of responsiveness through interactive features/feedback/user input options

**5. Target group: Is the app content (visual information, language, design) appropriate for your target audience?**

- 1 Completely inappropriate/unclear/confusing
- 2 Mostly inappropriate/unclear/confusing
- 3 Acceptable but not targeted. May be inappropriate/unclear/confusing
- 4 Well-targeted, with negligible issues
- 5 Perfectly targeted, no issues found

### SECTION B

**Functionality – app functioning, easy to learn, navigation, flow logic and gestural design of app**

**6. Performance: How accurately/fast do the app features (functions) and components (buttons/menus) work?**

- 1 App is broken; no/insufficient/inaccurate response (e.g. crashes/bugs/broken features, etc.)
- 2 Some functions work, but lagging or contains major technical problems
- 3 App works overall. Some technical problems need fixing/Slow at times
- 4 Mostly functional with minor/negligible problems
- 5 Perfect/timely response; no technical bugs found/contains a 'loading time left' indicator

**7. Ease of use: How easy is it to learn how to use the app; how clear are the menu labels/icons and instructions?**

- 1 No/limited instructions; menu labels/icons are confusing; complicated
- 2 Useable after a lot of time/effort
- 3 Useable after some time/effort
- 4 Easy to learn how to use the app (or has clear instructions)
- 5 Able to use app immediately; intuitive; simple

**8. Navigation: Is moving between screens logical/accurate/appropriate/ uninterrupted; are all necessary screen links present?**

- 1 Different sections within the app seem logically disconnected and random/confusing/navigation is difficult
- 2 Usable after a lot of time/effort
- 3 Usable after some time/effort
- 4 Easy to use or missing a negligible link
- 5 Perfectly logical, easy, clear and intuitive screen flow throughout, or offers shortcuts

**9. Gestural design: Are interactions (taps/swipes/pinches/scrolls) consistent and intuitive across all components/screens?**

- 1 Completely inconsistent/confusing
- 2 Often inconsistent/confusing
- 3 OK with some inconsistencies/confusing elements
- 4 Mostly consistent/intuitive with negligible problems
- 5 Perfectly consistent and intuitive

## **SECTION C**

### **Aesthetics – graphic design, overall visual appeal, colour scheme, and stylistic consistency**

**10. Layout: Is arrangement and size of buttons/icons/menus/content on the screen appropriate or zoomable if needed?**

- 1 Very bad design, cluttered, some options impossible to select/locate/see/read device display not optimised
- 2 Bad design, random, unclear, some options difficult to select/locate/see/read
- 3 Satisfactory, few problems with selecting/locating/seeing/reading items or with minor screensize problems
- 4 Mostly clear, able to select/locate/see/read items
- 5 Professional, simple, clear, orderly, logically organised, device display optimised. Every design component has a purpose

**11. Graphics: How high is the quality/resolution of graphics used for buttons/icons/menus/content?**

- 1 Graphics appear amateur, very poor visual design - disproportionate, completely stylistically inconsistent
- 2 Low quality/low resolution graphics; low quality visual design – disproportionate, stylistically inconsistent
- 3 Moderate quality graphics and visual design (generally consistent in style)
- 4 High quality/resolution graphics and visual design – mostly proportionate, stylistically consistent
- 5 Very high quality/resolution graphics and visual design - proportionate, stylistically consistent throughout

**12. Visual appeal: How good does the app look?**

- 1 No visual appeal, unpleasant to look at, poorly designed, clashing/mismatched colours
- 2 Little visual appeal – poorly designed, bad use of colour, visually boring
- 3 Some visual appeal – average, neither pleasant, nor unpleasant
- 4 High level of visual appeal – seamless graphics – consistent and professionally designed
- 5 As above + very attractive, memorable, stands out; use of colour enhances app features/menus

## **SECTION D**

### **Information – Contains high quality information (e.g. text, feedback, measures, references) from a credible source. Select N/A if the app component is irrelevant.**

**13. Accuracy of app description (in app store): Does app contain what is described?**

- 1 Misleading. App does not contain the described components/functions. Or has no description
- 2 Inaccurate. App contains very few of the described components/functions
- 3 OK. App contains some of the described components/functions
- 4 Accurate. App contains most of the described components/functions

- 5 Highly accurate description of the app components/functions
- 14. Goals: Does app have specific, measurable and achievable goals (specified in app store description or within the app itself)?**
- N/A Description does not list goals, or app goals are irrelevant to research goal (e.g. using a game for educational purposes)
- 1 App has no chance of achieving its stated goals
  - 2 Description lists some goals, but app has very little chance of achieving them
  - 3 OK. App has clear goals, which may be achievable.
  - 4 App has clearly specified goals, which are measurable and achievable
  - 5 App has specific and measurable goals, which are highly likely to be achieved
- 15. Quality of information: Is app content correct, well written, and relevant to the goal/topic of the app?**
- N/A There is no information within the app
- 1 Irrelevant/inappropriate/incoherent/incorrect
  - 2 Poor. Barely relevant/appropriate/coherent/may be incorrect
  - 3 Moderately relevant/appropriate/coherent/and appears correct
  - 4 Relevant/appropriate/coherent/correct
  - 5 Highly relevant, appropriate, coherent, and correct
- 16. Quantity of information: Is the extent coverage within the scope of the app; and comprehensive but concise?**
- N/A There is no information within the app
- 1 Minimal or overwhelming
  - 2 Insufficient or possibly overwhelming
  - 3 OK but not comprehensive or concise
  - 4 Offers a broad range of information, has some gaps or unnecessary detail; or has no links to more information and resources
  - 5 Comprehensive and concise; contains links to more information and resources
- 17. Visual information: Is visual explanation of concepts – through charts/graphs/images/videos, etc. – clear, logical, correct?**
- N/A There is no visual information within the app (e.g. it only contains audio, or text)
- 1 Completely unclear/confusing/wrong or necessary but missing
  - 2 Mostly unclear/confusing/wrong
  - 3 OK but often unclear/confusing/wrong
  - 4 Mostly clear/logical/correct with negligible issues
  - 5 Perfectly clear/logical/correct
- 18. Credibility: Does the app come from a legitimate source (specified in app store description or within the app itself)?**
- 1 Source identified but legitimacy/trustworthiness of source is questionable (e.g. commercial business with vested interest)
  - 2 Appears to come from a legitimate source, but it cannot be verified (e.g. has no webpage)
  - 3 Developed by small NGO/institution (hospital/centre, etc.) /specialised commercial business, funding body
  - 4 Developed by government, university or as above but larger in scale
  - 5 Developed using nationally competitive government or research funding (e.g. Australian Research Council, NHMRC)
- 19. Evidence base: Has the app been trialled/tested; must be verified by evidence (in published scientific literature)?**
- N/A The app has not been trialled/tested
- 1 The evidence suggests the app does not work
  - 2 App has been trialled (e.g., acceptability, usability, satisfaction ratings) and has partially positive outcomes in studies that are not randomised controlled trials (RCTs), or there is little or no contradictory evidence.
  - 3 App has been trialled (e.g., acceptability, usability, satisfaction ratings) and has positive outcomes in studies that are not RCTs, and there is no contradictory evidence.
  - 4 App has been trialled and outcome tested in 1-2 RCTs indicating positive results
  - 5 App has been trialled and outcome tested in > 3 high quality RCTs indicating positive results

## App subjective quality

### SECTION E

- 20. Would you recommend this app to people who might benefit from it?**

- 1 **Not at all** I would not recommend this app to anyone
- 2 There are very few people I would recommend this app to
- 3 **Maybe** There are several people whom I would recommend it to
- 4 There are many people I would recommend this app to
- 5 **Definitely** I would recommend this app to everyone

**21. How many times do you think you would use this app in the next 12 months if it was relevant to you?**

- 1 **None**
- 2 1-2
- 3 3-10
- 4 10-50
- 5 >50

**22. Would you pay for this app?**

- 1 No
- 3 Maybe
- 5 Yes

**23. What is your overall star rating of the app?**

- 1 Star: One of the worst apps I've used
- 2 .Stars
- 3 .Stars: Average
- 4. Stars
- 5 .Stars: One of the best apps I've used

These added items can be adjusted and used to assess the perceived impact of the app on the user's knowledge, attitudes, intentions to change as well as the likelihood of actual change in the target health behavior.

## **SECTION F: On A Scale of 1-5**

**(1:Strongly disagree 5:Strong agree)**

- 1. **Awareness:** This app is likely to increase awareness of the importance of addressing health related quality of life or well-being
- 2. **Knowledge:** This app is likely to increase knowledge/understanding of addressing health related quality of life or well-being
- 3. **Attitudes:** This app is likely to change attitudes toward improving addressing health related quality of life or well-being
- 4. **Intention to change:** This app is likely to increase intentions/motivation to address addressing health related quality of life or well-being
- 5. **Help seeking:** Use of this app is likely to encourage further help to enhance your health related quality of life or well-being
- 6. **Behavior change:** Use of this app is likely increase/decrease addressing health related quality of life or well-being

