### **2.3.2 Exploratory Objectives**

- 2.3.2.1 Caregiver and patient HRQOL, as assessed by the following PROMIS measures: Global Health, Profile 29+2 and 25, Companionship, Self-Efficacy for Managing Symptoms, Self-Efficacy for Managing Daily Activities, Positive Affect and Well-Being, and Emotional Support.
- 2.3.2.2 Caregiver and patient HRQOL, as assessed by the Perceived Stress Scale.
- 2.3.2.3 Caregiver and patient HRQOL, as assessed by the Resilience, Optimism and Gratitude scales
- 2.3.2.4 Patient (ages 8-17 years) and parent proxy for pediatric patients (ages 5-17 years) HRQOL, as assessed by measures of PROMIS sleep disturbance and Profile 25.
- 2.3.2.5 Caregiver and patient negative and positive dyadic interaction, as assessed by measures of the Dyadic Relationship Scale.
- 2.3.2.6 Caregiver and patient physical activity through physiological data capture using the wearable sensors.
- 2.3.2.7 Caregiver and patient health care utilization data (e.g., total count of hospital days, readmissions, and ambulatory care clinic visits).

- 2.3.2.8 Overall patient survival during first 120 days' post-HCT.
- 2.3.2.9 Obtain user experience of the Roadmap 2.0 app through the Mobile Application Rating Scale (MARS) and qualitative interviews.

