- 3.2.13 Health care utilization data. Patient health care utilization data (e.g., total count of hospital days, emergency department visits, readmissions, and ambulatory care clinic visits) will be captured through the electronic health record as well as self-report (i.e., if the patient is re-admitted at an outside hospital other than a participating site). Caregiver health care utilization data (e.g., hospital admissions, emergency department visits, and ambulatory care clinic visits) will be collected through self-report at the day 30 (+/-14) and day 120 (+/- 30) post-HCT PRO assessment period. The study team may access the electronic medical records for 1 year from the date of study enrollment.
- 3.2.14 Mobile Application Rating Scale (MARS) was added to the day 120 questionnaire to obtain user experience of the Roadmap 2.0 app.
- 3.2.15 Social Rhythms Application. We are interested in looking at how circadian rhythm may affect the participant's overall health. Participants may upload retroactive data from the Fitbit and will receive a personalized report about their circadian rhythm. Participant will be encouraged to upload their data at baseline (+/- 14 days), day 30 (+/- 14 days), and day 120 (+/- 30 days).

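### MARS Section F item 6 names an increase and a decrease in one agree/disagree statement, so its answers have no direction; it should be worded one way and kept out of any Section F mean until it is.

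*Combined protocol and SAP*

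**What the plan says.** Section 3.2.14 states that the MARS "was added to the day 120 questionnaire to obtain user experience of the Roadmap 2.0 app". The matching objective, 2.3.2.9, is to "Obtain user experience of the Roadmap 2.0 app through the Mobile Application Rating Scale (MARS) and qualitative interviews". Appendix D heads the form "Caregiver/Patients Day 120 (Ages 10 or older", so it goes to caregivers, adult patients and children from age 10.

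The form says that it rates app quality on four dimensions. These are Sections A to D, items 1 to 19. Section E adds four subjective-quality items (20 to 23). Six further items follow as Section F, introduced by "These added items can be adjusted and used to assess the perceived impact of the app" and scored "1:Strongly disagree 5:Strong agree". The sixth, labelled behavior change, is "Use of this app is likely increase/decrease addressing health related quality of life or well-being".

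In Section D, item 19 asks whether the app has been tested and adds that this "must be verified by evidence (in published scientific literature"; its anchors count randomised trials. Item 18 asks about the legitimacy of the source, and its top anchor refers to competitive research funding.

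Section 5.13.2 says only that questionnaires are scored by their coding manuals and that scores are compared between arms. It gives no rule specific to the MARS.

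**The concern.** An agreement item works only if it makes one claim. Item F6 makes two opposite claims. A respondent who expects the app to increase attention to quality of life can mark 5, and so can one who expects a decrease. Someone who thinks the app will change the behaviour in some unspecified way can mark 5 as well. No coding rule can separate these answers afterwards.

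The item is also the one closest to what the intervention is meant to do. If its answers enter a Section F mean, they blur the perceived-impact summary, including any comparison between arms or between caregivers and patients.

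Items 18 and 19 raise a milder worry. How an app was funded and whether trials of it have been published are facts about the app. They do not vary with a participant's use of it, so differences in the answers are likely to reflect knowledge or guessing.

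**Working it through.** The documents give no target, cut-off, power statement or score definition for the MARS, so there is no stated figure to reproduce. The check compares the Section F items and then bounds the effect of the flagged items.

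**Item wording.** F1, F2 and F4 each speak of an increase, F3 of a change in attitude towards improvement, and F5 of encouraging further help. Only F6 leaves both directions in place. Together with the lead-in, which says the items can be adjusted, this reads as an adaptation that was not finished. That is an inference from the form.

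**Item counts (Appendix D).** Section A has 5 items, B 4, C 3, D 7, E 4 and F 6.
- Sections A to D: 5 + 4 + 3 + 7 = 19.
- All sections: 19 + 4 + 6 = 29.

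**Effect of F6.** Assume simple item means. The largest error in a 1-5 item is 5 − 1 = 4.
- Share of Section F: 1/6 = 16.7%. Share of all items: 1/29 = 3.4%.
- Largest shift in one respondent's Section F mean: 4/6 = 0.67.
- Largest shift in a 29-item mean: 4/29 = 0.14.
- Shift in the A to D score: 0, because F6 is not in it.

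For a group, the shift in the Section F mean is at most p × 0.67, where p is the proportion who answered in the reverse sense. The documents do not give p. It can lie between 0 and 1, so the group shift lies between 0 and 0.67. As an illustration only, p = 10% gives 0.07.

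**Effect of items 18 and 19, on the same assumptions.**

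| Items flagged | Share of A to D | Largest shift, Section D mean | Largest shift, pooled A to D mean | Largest shift, mean of four section means |
|---|---|---|---|---|
| 19 only | 1/19 = 5.3% | 4/7 = 0.57 | 4/19 = 0.21 | 0.57/4 = 0.14 |
| 18 and 19 | 2/19 = 10.5% | 8/7 = 1.14 | 8/19 = 0.42 | 1.14/4 = 0.29 |

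With F6, 18 and 19 all set aside, 29 − 3 = 26 of 29 items (90%) remain.

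**The case against.** The strongest reply is that this is a wording slip in one exploratory questionnaire, and that the objective has other sources. Qualitative interviews are named beside the MARS, and Appendix D has separate feasibility and acceptability questions on whether the app was easy to set up and use. That stands as a limit on importance, although section 2.5.6 makes the interviews optional and the acceptability questions go only to caregivers and to patients older than 12. It does not make F6 interpretable.

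A reader might infer something stronger: that the MARS score does not measure user experience, because items 13, 14, 18 and 19 (4/19 = 21%) cannot be rated from using the app. The documents do not support this.
- F6 lies outside the four-dimension score. Sections A, B, C and E ask about engagement, ease of use, layout, recommendation and an overall rating. Even on this wider count, 29 − 5 = 24 of 29 items (83%) have neither defect.
- Items 14 and 18 say that the goals or source may be stated inside the app. A participant who downloads the app can compare it with its description for item 13.
- Section D offers N/A, with a printed line for items 14 and 19. This option means irrelevant, absent or untested rather than unable to judge, so it helps only in part.
- Children are few. Pediatric dyads number 40 of 300, so patients aged 10 to 17 are at most 40 of 600 participants (6.7%). The documents give no comprehension data for any age group.
- Guessing at a fact that is the same in both arms would mainly add noise. No bias between arms is shown.

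What remains is item 19, which plainly calls for outside literature, and arguably the funding anchor of item 18.

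**Conclusion.** The point holds for item F6. One of six perceived-impact items has no direction, which is worth at most 0.67 points on a simple Section F mean and nothing on the A to D quality score. For items 18 and 19 there is a case for a sensitivity summary but not for redesigning the instrument: 1 to 2 of 19 quality items, with a bound of 0.57 to 1.14 points on the Section D mean.

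These sizes are upper bounds. They assume simple item means, because the plan defines no MARS score, and full reversals, which the documents neither show nor exclude. That participants cannot answer items 18 and 19 well is a judgement drawn from the wording. The rest of the MARS remains usable for user experience. Only exploratory endpoint 3.2.14 is touched; the primary endpoint, the sample size and the type I error rate are not.

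**What to change.** 1. Word F6 in one direction, as a statement that the app is likely to increase the behaviour, in line with F1, F2 and F4. The form's own lead-in permits this.
2. Leave F6 answers collected under the present wording out of any Section F mean. If both wordings end up in the data, use the five-item mean (F1 to F5) for everyone, so that all respondents are scored on the same items, and report F6 separately by wording. If collection has ended, only this step applies.
3. Add a sentence to section 5.13.2: the Section D mean will be reported with all items and again without items 18 and 19, with the handling of N/A answers stated.

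The cost is one survey edit, one sentence in the analysis plan and one extra sensitivity summary. The loss is the F6 answers already given, which cannot be interpreted in any case. No item needs to be removed from the questionnaire, and the full Section D mean stays available.
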